17.1.10.11 Second Primary Malignancies

Second primary malignancies, including non-skin cancers, have been reported in patients treated with acalabrutinib. The most frequent second primary malignancy was skin cancer (squamous cell carcinoma of the skin). Monitor patients for the appearance of skin cancers. If a patient develops a second primary malignancy (other than non-melanoma skin cancer), discontinue acalabrutinib. Patients with a second primary malignancy should be managed according to institutional guidelines with diagnostic evaluations as clinically indicated.

17.1.10.12 Atrial Fibrillation/Flutter and Sinus Tachycardia

Atrial fibrillation/flutter have been reported in patients treated with acalabrutinib. Atrial fibrillation has also been observed in patients treated with AZD4573, although positive causality has not been established.

CC1

17.1.10.13 Infection/Bone Marrow Toxicity with Peripheral Effect / Lymphoid Tissue Hypocellularity

Infection/bone marrow toxicity with peripheral effect/lymphoid tissue hypocellularity is an important potential risk for AZD4573, based on findings in preclinical studies. Severe infection is considered as an important risk with the combination therapy (Section [17.1.10.7](#)).

As observed in preclinical studies, this important potential risk refers to haematological changes (decreased platelets, red blood cell count/haematocrit, reticulocytes, neutrophils, lymphocytes) that may be/may not be accompanied by secondary infections.

AEs of thrombocytopenia should be managed as deemed appropriate by the Investigator as per standard institutional guidelines and in some cases, management of thrombocytopenia may require platelet transfusions, again these should be done according to local hospital guidelines. If indicated, transfusions or growth factors can be administered during the screening period, but such cases of deterioration of haematological function must be discussed with the Medical Monitor, to confirm start of study treatment.

Common treatable causes of anaemia (eg, iron, vitamin B12, or folate deficiencies and hypothyroidism) should be excluded. In some cases, management of anaemia may require blood transfusions which should be given as per local institutional guidelines.

17.1.10.14 Pancreatic and Cortical Adrenal Injury (as well as Surveillance for Renal, Thymus, and Spleen Toxicity)

Pancreatic injury and cortical adrenal injury are potential risks for AZD4573 based on preclinical observations, however, to date, there are no clinical data suggestive of these risks, but safety surveillance will continue.

Regular complete blood counts, clinical chemistry and coagulation tests will be performed throughout the conduct of the study to monitor for any abnormal laboratory parameters, for example; monitoring of lipase and amylase levels for potential pancreas toxicity, creatinine values and regular urinalysis testing for kidney function, potassium, sodium, cortisol levels along with adrenocorticotrophic hormone levels for adrenal glands and thyroid-stimulating hormone (TSH) for any thyroid toxicity.

17.1.10.15 Drug-Drug interactions

Specific drug-drug interaction studies have not yet been performed for AZD4573. For guidance please refer to Section 15.11.

Acalabrutinib may be affected by agents that reduce gastric acidity (antacids or proton-pump inhibitor). Acalabrutinib is not a strong direct inhibitor or inducer of CYP isoforms and is therefore unlikely to perpetrate drug-drug interactions through affecting CYP isoforms (see Section 15.11).

17.1.10.17 Management of Other Events: Infusion Site Reactions

As with other drugs administered intravenously, local infusion site reactions (eg, infusion pain, infusion site reaction, skin or vein irritation) may occur and these can be managed according to local institutional guidelines. Implantable port insertions (eg, Portacath) may be considered.

17.2 Adverse Events and Serious Adverse Events

A formal assessment of AEs will occur at the visits marked in the SoA (Section 10.2), but AEs reported at any time during the study must also be recorded in the eCRF.

Please refer to Section 8.2.

17.2.1 Adverse Events of Special Interest for Acalabrutinib

The following events are Adverse Events of Special Interest (AESIs) for acalabrutinib and must be reported to the Sponsor expeditiously, irrespective of regulatory seriousness criteria or causality:

- Ventricular arrhythmias (eg, ventricular extrasystoles, ventricular tachycardia, ventricular arrhythmia, ventricular fibrillation)

Adverse events of special interest for AZD4573 are described in Section 8.2.11.

17.3 Overdose

Please refer to Section 8.3 for general information and information related to AZD4573.

An acalabrutinib overdose is defined as any dose that is higher than the investigated dose. For any patient experiencing an acalabrutinib overdose, observation for any symptomatic side

effects should be instituted, and vital signs, biochemical and haematological parameters should be followed closely (consistent with the protocol or more frequently, as needed). Appropriate supportive management to mitigate adverse effects should be initiated. If the overdose ingestion of acalabrutinib is recent and substantial, and if there are no medical contraindications, use of gastric lavage or induction of emesis may be considered.

17.4 Efficacy Assessments

All assessments of anti-tumour activity will be done by the investigators using standard response criteria as specified below ([Table 18](#)).

17.4.1 Disease Assessment Criteria

Disease staging at baseline for DLBCL and MZL will be done by a modified Ann Arbor classification system ([Table 17](#); [Cheson et al 2014](#)). Response assessments will be done by the investigator using standard Lugano 2014 response criteria as specified in [Table 18](#).

Table 17 Lugano Modification of Ann Arbor Staging System (for Primary Nodal Lymphomas)

Stage		Involvement	Extranodal (E) Status
Limited	I	One node or a group of adjacent nodes	Single extranodal lesions without nodal involvement
	II	Two or more nodal groups on the same side of the diaphragm	Stage I or II by nodal extent with limited contiguous extranodal involvement
II Bulky Whether stage II bulky disease is treated as limited or advanced disease may be determined by histology and a number of prognostic factors		II as above with “bulky” disease	Not applicable
Advanced	III	Nodes on both sides of the diaphragm; nodes above the diaphragm with spleen involvement	Not applicable
	IV	Additional noncontiguous extralymphatic involvement	Not applicable

Note: Extent of disease is determined by PET-CT for avid lymphomas and CT for nonavid histologies.
Tonsils, Waldeyer's ring, and spleen are considered nodal tissue.

Abbreviations: CT = computed tomography; PET = positron emission tomography.

Reproduced from Table 2.

Table 18 The Lugano Response Criteria for Non-Hodgkin's Lymphoma

Response and Site	PET-CT-Based Response	CT-Based Response
Complete:	Complete metabolic response:	Complete radiologic response (all of the following):
Lymph nodes and extralymphatic sites	Score 1, 2, or 3 ^a with or without a residual mass on 5PS ^{b,c} It is recognised that in Waldeyer's ring or extranodal sites with high physiologic uptake or with activation within spleen or marrow (eg, with chemotherapy or myeloid colony-stimulating factors), uptake may be greater than normal mediastinum and/or liver. In this circumstance, complete metabolic response may be inferred if uptake at sites of initial involvement is no greater than surrounding normal tissue even if the tissue has high physiologic uptake	Target nodes/nodal masses must regress to ≤ 1.5 cm in LDi No extralymphatic sites of disease
Nonmeasured lesion	Not applicable	Absent
Organ enlargement	Not applicable	Regress to normal
New lesions	None	None
Bone marrow	No evidence of FDG-avid disease in marrow	Normal by morphology; if indeterminate, IHC negative
Partial:	Partial metabolic response:	Partial remission (all of the following):
Lymph nodes and extralymphatic sites	Score 4 or 5 ^b with reduced uptake compared with baseline and residual mass(es) of any size	$\geq 50\%$ decrease in SPD of up to 6 target measurable nodes and extranodal sites
	At interim, these findings suggest responding disease	When a lesion is too small to measure on CT, assign 5 mm \times 5 mm as the default valve
	At end of treatment, these findings indicate residual disease	When no longer visible 0 \times 0 mm For a node > 5 mm \times 5 mm, but smaller than normal, use actual measurement for calculation
Nonmeasured lesions	Not applicable	Absent/normal, regressed, but no increase
Organ enlargement	Not applicable	Spleen must have regressed by $> 50\%$ in length beyond normal
New lesions	None	None

Response and Site	PET-CT-Based Response	CT-Based Response
Bone marrow	Residual uptake higher than uptake in normal marrow but reduced compared with baseline (diffuse uptake compatible with reactive changes from chemotherapy allowed). If there are persistent focal changes in the marrow in the context of a nodal response, consideration should be given to further evaluation with MRI or biopsy or an interval scan	Not applicable
No response or stable disease:	No metabolic response:	Stable disease:
Target nodes/nodal masses, extranodal lesions	Score 4 or 5 with no significant change in FDG uptake from baseline at interim or end of treatment	< 50% decrease from baseline in SPD of up to 6 dominant, measurable nodes and extranodal sites; no criteria for progressive disease are met
Nonmeasured lesions	Not applicable	No increase consistent with progression
Organ enlargement	Not applicable	No increase consistent with progression
New lesions	None	None
Bone marrow	No change from baseline	Not applicable
Progressive disease:	Progressive metabolic disease:	Progressive disease requires at least 1 of the following PPD progression:
Individual target nodes/nodal masses	Score 4 or 5 with an increase in intensity of uptake from baseline and/or	An individual node/lesion must be abnormal with: LDi > 1.5 cm and Increase by $\geq 50\%$ from PPD nadir and An increase in LDi or SDi from nadir 0.5 cm for lesions ≤ 2 cm 1.0 cm for lesions > 2 cm

Response and Site	PET-CT-Based Response	CT-Based Response
Extranodal lesions	New FDG-avid foci consistent with lymphoma at interim or end-of-treatment assessment	In the setting of splenomegaly, the splenic length must increase by > 50% of the extent of its prior increase beyond baseline (eg, a 15 cm spleen must increase to > 16 cm). If no prior splenomegaly, must increase by at least 2 cm from baseline New or recurrent splenomegaly
Nonmeasured lesions	None	New or clear progression of pre-existing nonmeasured lesions
New lesions	New FDG-avid foci consistent with lymphoma rather than another aetiology (eg, infection, inflammation). If uncertain regarding aetiology of new lesions, biopsy or interval scan may be considered	Regrowth of previously resolved lesions A new node > 1.5 cm in any axis A new extranodal site > 1.0 cm in any axis; if < 1.0 cm in any axis, its presence must be unequivocal and must be attributable to lymphoma Assessable disease of any size unequivocally attributable to lymphoma
Bone marrow	New or recurrent FDG-avid foci	New or recurrent involvement

^a The Lugano 2014 criteria are used in this study for disease assessment. In line with these criteria, it should be clarified that the study definition of CMR is a Deauville score 1-3.

^b A score of 3 in many participants indicates a good prognosis with standard treatment, especially if at the time of an interim scan. However, in trials involving PET where de-escalation is investigated, it may be preferable to consider a score of 3 as inadequate response (to avoid under treatment). Measured dominant lesions: Up to 6 of the largest dominant nodes, nodal masses, and extranodal lesions selected to be clearly measurable in 2 diameters. Nodes should preferably be from disparate regions of the body and should include, where applicable, mediastinal and retroperitoneal areas. Non-nodal lesions include those in solid organs (eg, liver spleen, kidneys, and lungs), GI involvement, cutaneous lesions, or those noted on palpation. Nonmeasured lesions: Any disease not selected as measured, dominant disease and truly assessable disease should be considered not measured. These sites include any nodes, nodal masses, and extranodal sites not selected as dominant or measurable or that do not meet the requirements for measurability but are still considered abnormal, as well as truly assessable disease, which is any site of suspected disease that would be difficult to follow quantitatively with measurement, including pleural effusions, ascites, bone lesions, leptomeningeal disease, abdominal masses, and other lesions that cannot be confirmed and followed by imaging. In Waldeyer's ring or in extranodal sites (eg, GI tract, liver, bone marrow), FDG uptake may be greater than in the mediastinum with complete metabolic response, but should be no higher than surrounding normal physiologic uptake (eg, with marrow activation as a result of chemotherapy or myeloid growth factors).

^c PET 5PS: 1, no uptake above background; 2, uptake ≤ mediastinum; 3, uptake > mediastinum but ≤ liver; 4, uptake moderately > liver; 5, uptake markedly higher than liver and/or new lesions; X, new areas of uptake unlikely to be related to lymphoma.

Abbreviations: 5PS = 5-point scale; CT = computed tomography; CMR = complete metabolic response; FDG = fluorodeoxyglucose; GI = gastrointestinal; IHC = immunohistochemistry; LD_i = longest transverse diameter; MRI = magnetic resonance imaging; PET = positron-emission tomography; PPD = product of the perpendicular diameters; SD_i = shortest axis perpendicular to LD_i; SPD = sum of the product of the diameters. [Cheson et al 2014](#)

17.4.2 Disease Assessment Schedule

Baseline tumour assessments will be performed using radiologic imaging by computed tomography (CT) with contrast and positron- emission tomograph (PET)-CT during the screening period. CT scans with contrast will cover neck, chest, abdomen, pelvis and any other disease sites; PET scans will cover the whole body from base of skull to mid-thigh.

Radiologic scans (ie, contrast CT) and PET scans will be performed as specified in [Table 19](#), to confirm CR or as clinically indicated. Unscheduled radiologic scans may be performed at Investigator discretion if deemed clinically indicated.

Table 19 Radiologic Scans and PET Scans for Tumour Assessments

Timepoints		Required Radiologic Scans ^a	
Screening		Contrast CT	PET
During study ^b	After 8 weeks (~2 cycles)	Contrast CT	PET
	After 17 weeks (~5 cycles)	Contrast CT	
	After 26 weeks (~8 cycles)	Contrast CT	PET
	After 38 weeks (~12 cycles)	Contrast CT	
	After 50 weeks (~16 cycles)	Contrast CT	PET
	After 62 weeks (~20 cycles)	Contrast CT	
	After 74 weeks (~24 cycles)	Contrast CT	PET
	After 86 weeks (~28 cycles)	Contrast CT	
	After 98 weeks (~32 cycles)	Contrast CT	PET
	Every 12 weeks (~4 cycles) thereafter until the end of the study	Contrast CT	
Every 24 weeks (~8 cycles) thereafter until the end of the study		Contrast CT	PET
30-day Follow-up visit ^c		Contrast CT	PET

^a Following complete metabolic response, subsequent scheduled PET assessments are no longer mandatory.

^b Window of \pm 1 week for all timepoints.

^c Tumour assessments will be repeated at this visit for discontinued participants if not previously performed within the required timeframe ie, 9 weeks for participants that discontinued before or during Week 26, and 12 weeks for those that discontinued after Week 26.

If a PET-CT is not available, an independent PET and a diagnostic quality CT scan (with contrast) can be used. If PET and CT scans are done on the same day, the PET must be performed prior to the contrast-enhanced CT not to compromise the PET read-out.

Post-screening, the CT portion of a PET-CT (without contrast) may replace a contrast CT per local institutional practice; however, certain radiographic requirements are needed for acceptance, as described in the Site Radiology Manual, provided separately from this protocol.

Where contrast CT is contraindicated or unobtainable, MRI or CT (without contrast) with diagnostic quality (sufficient resolution to allow bi-dimensional measurements) may be used instead. In cases where MRI is desirable, the MRI must be obtained at baseline and at all subsequent response evaluations.

Following complete metabolic response, subsequent scheduled PET assessments are no longer mandatory. For participants with baseline hepatosplenomegaly, the cranial-caudal measurement of the spleen and longest diameter of the liver will be assessed at Screening and all subsequent response evaluations.

All response assessments will be made by the Investigator. All images for the assessment of response will be collected and stored for central review.

Participants should have radiographic tumour measurements done at the participating study centre or an acceptable alternate imaging facility using an identical imaging protocol and similar equipment. The same imaging equipment should be used for all scans whenever possible. The same radiologist should be assigned to read all the scans for a given participant throughout the study.

Participants who discontinue study intervention for reasons other than PD will continue to be scanned for disease response following the same schedule until documented PD, regardless of the start of new anti-lymphoma treatment.

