Assessment	Screen ^a	Cycle 1, Weeks 1-5 (includes intra- patient Dose ramp up)	Cycles 2-8 (Cycle=21 Days)			Cycles 9+ (Cycle = 21 days) ⁱⁱ	Disease Assessment ^b / End of Treatment ^{mm}	30-Day SFU ^c	LTFU	Details in CSP Section					
			Days												
			1	8	15										
		(±2 Days)	(±2 Days)			(-2 to +5 Days)	(±7 Days)	(±7 Days)							
Bone marrow biopsy & aspirate ^{gg}	X						As clinically indicated and to confirm CR			Section 17.4.3 and Section 17.10.3					
Disease assessment ^b and radiologic scans ^{hh}	X	See Table 19 for schedule						X		Section 17.4.2					
Acalabrutinib oral, BID ⁱⁱ		Twice daily (from Cycle 1, Week 1 to end of treatment)								Section 15.1					
AZD4573 intravenous ^{jj}		Once weekly (from Cycle 1, Week 1 to end of treatment) ⁿⁿ								Section 15.1					
Acalabrutinib drug accountability ^{kk}		X	X	X	X	X				Section 15.8					
Disease progression follow-up (SoC)									X	Section 17.1.9.2					
Survival Follow-up									X	Section 17.1.9.3					

- ^a Screening tests should be performed within 30 days before the first administration of study drug, unless otherwise indicated.
- ^b Disease assessments will be done by the Investigator using the Lugano Response Criteria for Non-Hodgkin's Lymphoma ([Cheson et al 2014](#)). Additional disease assessments may be performed as clinically indicated.
- ^c The SFU visit will be performed 30 days (± 7 days) after the last dose of all study drug. Tumour assessments will be repeated at this visit if they have not been performed within 9 weeks if the participant discontinued before or during Week 26, or 12 weeks if the participant discontinued after Week 26.
- ^d Informed consent must be obtained \leq 30 days before the first dose of study drug and must be obtained before any protocol-defined screening procedures are done.
- ^e Vital signs (blood pressure, pulse rate, temperature) will be assessed after the participant has rested for at least 10 mins. Blood pressure and pulse rate will be measured at Screening, and on Day 1 of Cycle 1, Weeks 1-3 at the following timepoints: predose (within 2 h prior to infusion), 1 h after the start of the infusion (± 10 mins), at end of infusion (up to 10 mins post dose) and then 4 h (± 30 mins) and 6 h (± 30 mins) after start of infusion, from Cycle 1 Week 4 onwards, at predose (up to 30 mins prior to infusion), at the end of infusion (up to 30 mins post dose), and at the 30-day SFU. Temperature to be taken pre-infusion (up to 2 h prior to all infusions).

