11.3.3 Overall Benefit/Risk Conclusion

Eligible participants will be r/r to prior treatments for their disease and considered to have no alternative treatment options available to them. Furthermore, participants will have varying levels of disease burden at study entry and almost certainly have acquired mutations as part of their disease course. Therefore, there is no guarantee that any participant will derive clinical benefit during this study.

AstraZeneca believes the anticipated benefits that may be afforded to participants with r/r haematological malignancies currently outweigh the identified and potential risks associated with AZD4573 in combination with acalabrutinib.

As described, the study design aims to minimise risks and build on the preliminary efficacy seen to date in the ongoing FTIH study (D8230C00001), reflecting clinical responses in a r/r participant population. Thus, the benefit/risk assessment for this Phase I/II combination study is considered acceptable for participants for whom there is no alternative standard therapy.

For an assessment of benefit and risks pertaining to the conduct of this study during the COVID-19 pandemic, refer to Appendix [A 11](#).

12 OBJECTIVES AND ENDPOINTS – MODULE 1

Objectives and Endpoints for Part A and Part B are outlined in [Table 7](#).

Table 7 Objectives and Endpoints – Module 1

Objectives	Endpoints
Primary	
Part A	

 Assess the safety and tolerability, describe the DLTs, and identify the MTD and/or RP2D of AZD4573 in combination with acalabrutinib (100 mg BID) 	
 Adverse events, DLTs, laboratory data, vital signs, and ECG changes
Part B	

 Assess the efficacy of AZD4573 in combination with acalabrutinib by evaluation of objective response rate 	
 Endpoint based on revised response criteria for malignant lymphoma (Cheson et al 2014): 
 ORR, defined as the proportion of participants who have a tumour response (CR and PR)^a
Secondary	
Part B	

 Assess efficacy of AZD4573 in combination with acalabrutinib by evaluation of tumour response and overall survival 	
 Endpoints based on revised response criteria for malignant lymphoma (Cheson et al 2014): 
 CR rate DoR TTR PFS OS

Objectives	Endpoints

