17.1.9.2 Long-term Follow-up Visits

Participants who discontinue both study drugs before documented disease progression will be followed according to SoC until documented disease progression or the start of new anti-cancer therapy. Disease progression or start of new anti-cancer therapy will be captured in the eCRF. During this period, only information on any SAEs considered related to IP or study procedures will be collected. If a participant is unable to attend site for this visit, the long-term follow-up may be performed via phone call. Long-term follow-up visits will cease at disease progression or start of a new anti-cancer therapy, whichever comes first. The long-term follow-up will not apply to participants who withdraw consent or are lost to follow-up.

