17.1.9.3 Survival Follow-up

All participants will be followed for survival until death, loss to follow-up, AstraZeneca closes the study, or withdrawal of consent, whichever occurs first. Participants will be followed for survival by telephone calls or clinic visits approximately every 3 months. Site personnel will attempt to collect the vital status of the participant within legal and ethical boundaries for all participants who received investigational product. Public sources may be searched for vital status information. If vital status is determined as deceased, this will be documented and the participant will not be considered lost to follow-up. Sponsor personnel will not be involved in

any attempts to collect vital status information. During this period, information will be collected in the eCRF on survival status and any new anti-cancer therapies, and on any SAEs considered related to study drug(s) or study procedures.

The follow-up calls/clinic visits for survival should occur every three months, starting 3 months after end of treatment/discontinuation (ie, 3/6/9/12 months after treatment). In case a shorter/longer interval between two follow-up calls occurs the frequency should return to the multiple of 3 months after treatment (eg, 3/6/9/12 months after treatment and so on).

In preparation for an analysis, survival calls will be made in the week following the data-cut-off for the analysis.

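### Sections 17.4.2 and 17.1.9.2 give conflicting tumour-assessment rules for participants who stop treatment without progression

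*Protocol*

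**What the plan says.** Section 17.4.2 covers participants who stop study intervention for a reason other than PD. It says that they "will continue to be scanned for disease response following the same schedule until documented PD, regardless of the start of new anti-lymphoma treatment". The schedule meant is Table 19: scans after Weeks 8, 17 and 26, then every 12 weeks to Week 98, each with a window of one week either side. After that the table continues: "Every 12 weeks (~4 cycles) thereafter until the end of the study".

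Section 17.1.9.2 covers participants who stop both study drugs before documented PD. They "will be followed according to SoC until documented disease progression or the start of new anti-cancer therapy". It adds: "Long-term follow-up visits will cease at disease progression or start of a new anti-cancer therapy, whichever comes first". For a participant who cannot come to the site, "the long-term follow-up may be performed via phone call".

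The Schedules of Activities for Part A (Table 4) and Part B (Table 5) follow Section 17.1.9.2. For disease status, their long-term follow-up column marks the row "Disease progression follow-up (SoC"), which refers to that section. The imaging row is marked at the 30-day safety follow-up but not at long-term follow-up.

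In survival follow-up (Section 17.1.9.3), "information will be collected in the eCRF on survival status and any new anti-cancer therapies", together with treatment-related SAEs. Progression is not on the list.

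**The concern.** Both rules cover a participant who stops both drugs without PD, and a site cannot follow both. Section 17 makes adherence to the Schedule of Activities mandatory and allows no waivers. A site that works from Table 4 or 5 therefore has good reason to stop protocol imaging after the 30-day visit. A site that works from Section 17.4.2 has equally good reason to continue it.

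The date of PD, and whether PD is documented at all, feeds PFS and DoR, which are secondary in Part B and exploratory in Part A (Table 7). It also feeds the data cut-off rule in Sections 13.1 and 13.4, one arm of which counts participants who have progressed or died. With no control group, a difference in how PD is ascertained is not balanced out by a comparison.

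**Working it through.** The plan gives no figure to reproduce. The check sets the two rules side by side for each kind of participant. Rule A is Section 17.4.2. Rule B is Section 17.1.9.2 with Tables 4 and 5.

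| Participant | Rule A | Rule B | Conflict |
|---|---|---|---|
| Stops both drugs at PD | No further scans for PD | Does not apply | None |
| Stops both drugs, no PD, no new therapy | Table 19 scans to PD | Standard of care to PD, phone allowed | Interval |
| Stops both drugs, no PD, later starts new therapy | Table 19 scans to PD | Standard of care, ends when new therapy starts | Interval and stopping point |
| Stops because alternative anti-cancer therapy starts (a discontinuation reason in Section 7.1) | Table 19 scans to PD | No progression follow-up beyond the 30-day visit | Interval and stopping point |

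**Interval.** Under Rule A the planned gaps are 17 − 8 = 9 weeks and 26 − 17 = 9 weeks, then 38 − 26 = 12 weeks. With one week of tolerance at each end, two attended scans are at most 9 + 2 = 11 weeks apart up to Week 26 and 12 + 2 = 14 weeks apart after it. (For MZL, Section 17.4.4 relaxes CT to every 24 weeks after the first year.) Rule B sets no bound, and a telephone contact includes no scan. Standard-of-care imaging could be more or less frequent than Table 19, so the direction of any shift in the PD date is not determined.

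**Stopping point.** Under Rule B, PD after new therapy has no stated route into the database, because long-term follow-up has ended and Section 17.1.9.3 does not list progression. Under Rule A it is captured.

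**Precedence.** The precedence statement in Sections 5.1 and 14 concerns core against module eligibility criteria. It does not help here, since both conflicting sections belong to Module 1.

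**Cut-off trigger.** In a planned subtype cohort of about 21 (Section 13.1), 75% is 0.75 × 21 = 15.75, so 16 participants. PD that goes undocumented can only postpone that count. The alternative criterion of about 6 months, whichever comes first, limits the delay.

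**Scale.** One participant is 1/21 = 4.8% of a planned subtype cohort. Recruitment was halted, and the text available does not give the number enrolled. The protocol also gives no rate of stopping without PD and no rate of new therapy before PD, so the number affected cannot be calculated.

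**The case against.** The strongest reply is that Section 17.1.9.2 governs visits, not scans. It does not mention imaging, and the imaging row of Tables 4 and 5 points to Table 19. On that reading a site scans under 17.4.2 and merely telephones under 17.1.9.2. This does not hold. Section 17.1.9.2 states how progression is to be followed and when that follow-up ends, the Schedules of Activities repeat the standard-of-care label, and they mark no imaging at long-term follow-up. What does stand is that neither place expressly forbids imaging, and that both rules run to documented PD unless new therapy comes first.

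It is also fair to say that the 30-day visit requires a tumour assessment if none is recent, so Rule B does not lose everything after the last dose.

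Three stronger conclusions are tempting, and the documents do not support them.

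- A reader might infer that responses to the next therapy will enter the response rates, because 17.4.2 continues scanning for response and Table 7 sets no time limit: "ORR, defined as the proportion of participants who have a tumour response (CR and PR"). But being scanned is not the same as being counted. Section 18.4.5, which the amendment summary says was clarified on response and DoR, was not in the text available and may settle this.
- A reader might infer that PFS and DoR are informatively censored at new therapy. Section 17.1.9.2 sets follow-up, not censoring. The censoring rule also belongs to Section 18.4.5.
- A reader might attach a size, taking the unknown best responses in Section 2.2.6 (4 of 17 with DLBCL, 13 of 38 overall) as the rate of stopping without PD. Those come from a different, monotherapy study and describe missing responses, not discontinuation. A rate of new therapy would have to be invented as well.

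Halted recruitment does not remove the problem. Participants already enrolled are followed until data collection for the primary analysis ends, and missed scans cannot be recovered.

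**Conclusion.** The contradiction is real and stands in current text. For participants who stop both drugs without PD, the protocol gives two assessment intervals and two stopping points and does not say which applies. PFS, DoR and the count behind the 75% trigger can therefore depend on which section a site follows.

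The size is unknown and cannot be derived from the protocol. Only participants who stop without PD are affected, and the stopping-point conflict matters only for those of them who start new therapy before PD. If Section 18.4.5 censors PFS and DoR at new therapy and excludes later responses, the stopping-point conflict loses most of its weight in the analysis. The interval conflict remains whatever that section says.

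This is an internal inconsistency worth correcting. On the text available it is not a defect that by itself invalidates the analysis.

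**What to change.** State one tumour-assessment rule for participants who stop without PD, in the same terms in Section 17.4.2, Section 17.1.9.2 and the long-term follow-up column of Tables 4 and 5. Keeping Table 19 imaging until PD or death preserves the most information, since PD after new therapy is then observed and the analysis can still censor earlier if it wishes. The long-term follow-up row would then cite Table 19 instead of standard of care.

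Align that rule with the PFS and DoR censoring rule in Section 18.4.5. Confirm there that responses first seen after new anti-lymphoma therapy are not counted as study responses.

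The same edit should reconcile the 30-day re-scan threshold. It is Week 53 in Section 17.1.9.1 but Week 26 in the footnotes to Tables 4, 5 and 19.

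The cost is wording in a few places. Section 17.4.2 already requires the imaging, so extra scans arise only where sites had been following Section 17.1.9.2, and only up to the end of data collection.
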